E-PrEP Cluster-RCT Study Protocol

Background

Of the estimated 50,000 new HIV infections occurring annually in the U.S., Men who have Sex with Men (MSM), who make up 2-3% of the population, account for 61% of cases. Disparities affecting Young Men who have Sex with Men (YMSM), and particularly Young Men of Color who have Sex with Men (YMCSM), are even more pronounced. In 2009, YMSM accounted for 69% of all new HIV cases in young people, and 27% of overall new HIV infections.⁵² While HIV rates have stabilized or decreased for most demographic groups in the U.S., they continue to rise among YMCSM.^{52,54,55} Between 2006-2009, there was a 34% increase in new HIV infections in YMSM, with Black MSM experiencing a 48% increase.⁵² Other studies have found very high incidence rates in YMCSM, ranging up to 5.8% annually.^{71,72} In the Bronx, the epidemic parallels national trends, with YMCSM accounting for 65% of all new HIV cases in young people.^{54,55}

Reasons for increasing rates of HIV in YMCSM are multiple and complex. Lack of access to regular medical care or to antiretroviral therapy, higher community viral loads, lack of knowledge of HIV status, stigma and discrimination surrounding both same sex behaviors and HIV, complacency about HIV risk, and failure of effective prevention tools to reach YMCSM all contribute to the growing epidemic.^{71,73,74} While PrEP does not address all of these factors directly, it may mitigate the immediate risk of HIV acquisition in YMCSM.⁶¹

While many effective behavioral HIV prevention interventions have been developed, these programs do not reach nearly 75% of YMSM.⁵⁹ This lack of reach may partly be explained by inability to reach those YMCSM who do not identify as gay or bisexual and/or who are unlikely to present in-person to LGBT- or HIV-affiliated settings, where most interventions take place.^{56,57} Bio-behavioral interventions, including PrEP, that can be publicized in widely accessible venues (e.g. social media) and delivered in general medical (e.g. primary care) settings are urgently needed to help reduce the HIV burden in YMCSM.⁷⁵⁻⁷⁸

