Baseline Survey T1						
Exposure to Intervention						
Assessment T2 (intervention end)						
Assesment T3 (Post-intervention)						
Assesment T4 (Follow-Up)						

Developing BxNow (control condition): BxNow will focus on general health topics unrelated to HIV or sexual health (i.e. fitness, nutrition, smoking), but will also include basic information on PrEP as well as referral resources. We will develop a 6-week timeline to match the E-PrEP timeline, and we will compile publicly available digital media addressing general health topics (e.g. from CDC LGBT website). As with E-PrEP, standardized BxNow content will be delivered by Peers, using their own language. Additionally, after trial end (12 weeks), BxNow participants will be exposed to all E-PrEP components.

Setup of intervention sites: We will provide customized training and setup to the project team (PI, RA, Peers), establish 'E-PrEP' and 'BxNow' (control) private virtual communities (e.g closed Facebook group, private Twitter feed, private Tumbler blog), and implement systems for recruitment, consent, and online data collection (e.g. # of sites joined by each participant, engagement indicators for each posted component and for each participant, and other process measures).

Risk: Possible risks faced by the participant include: confidentiality issues, inconvenience and discomfort associated with interviews, potential risk compensation if PrEP is adopted, and fear that refusal to participate will affect relationship with Peers. More detail information about the potential risk and precautions against those risks can be found in the attached Protection of Human Subjects document sections I.4 and I.5.

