7. The screening page will be a very brief online questionnaire. Those meeting eligibility will be taken to an informed consent or assent (if <18 years of age) page, provided with contact information of the PI and research assistant to enable them to ask questions about the study prior to joining. Those not meeting eligibility will be taken to a separate page indicating that they were not eligible (but will not say why, to prevent fraudulent “gaming” of the study) and provided with links to local health resources.
8. To help facilitate understanding of the research study and consent procedures, we will record brief streaming videos of the consent in English and Spanish in addition to having the consent text on the informed consent page. We will provide potential participants with contact information (email, social media messaging link, and telephone) of the PI and research assistant to enable them to ask questions about the study prior to joining. Participants will indicate their consent by entering their social media ID and clicking a button to that effect. Participants will be able to print the consent document or have it emailed to them. After indicating consent, participants will be taken directly to an online baseline survey. Those indicating they do not agree will be taken to a separate page and provided links to local health resources.
9. We will obtain online informed consent prior to providing the self-administered online questionnaires and collection of any automated collection of process data. Online informed consents will be provided in two ways: (1) A recorded video of the informed consent text by a Peer will be displayed and (2) the same information will be provided in an easy to read text format. A link for emailing or direct messaging and contact information with the PI and Research Assistant’s office phone numbers will be displayed for potential participants to ask any questions they may have. To indicate consent, an individual will then click a box attesting to their consent and then clicking a “submit” button. After consenting, participants will be taken directly to a baseline assessment survey and after completing the survey, participants will be asked to join the private social media E-PrEP (intervention) or BxNow (control condition) groups on one or more of three social media sites.

More detail information about recruitment practices and ethical research considerations can be found in the (I.4 and I.5)

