Effectiveness measures will come from the online assessments/surveys collected at 0, 6, 12 weeks. We will use a HIPAA compliant web survey software (i.e. SurveyGizmo.com) to collect survey data. This information is stored on HIPAA compliant, encrypted cloud servers. The data will be downloaded to the PI’s secure password protected office computer. Surveys will not contain personal identifiers, but will contain a study ID associated with a participant’s social media profile. The “Key” associating the study ID to a participant’s social media profile will be kept in a password protected encrypted file on the PI’s office computer. It will not be possible using the survey data for anyone to figure out the actual or online identity of a participant. We will also collect de-identified IP addresses to aid us in identifying potentially duplicate respondents.

I.3. Vulnerable population. Young men who have sex with men could be vulnerable due to their status as a **stigmatized population in society and further stigmatization could be possible if their status as a participant in an HIV prevention intervention is revealed.** In the following sections, we discuss these risks and procedures to minimize them and believe that the risks to participation in the proposed study are minimal.

I.4. Potential risks to subjects. We believe that the risks posed to participation in our study are minimal and no greater than what individuals encounter in their regular use of the Internet and social media sites. The primary risks of this study are: (1) breach of confidentiality leading to embarrassment or “outing” of an individual’s sexual orientation, (2) breach of confidentiality leading to disclosure of an individual’s participation in a HIV prevention intervention, (3) inconvenience and discomfort associated with interviews, and (4) potential side effects related to the uptake of PrEP

Confidentiality issues: We will collect limited personal information from participants to facilitate follow-up and will be asking personal questions about substance use, HIV risk behaviors, and sexual identity and orientation. We have outlined procedures to address maintaining confidentiality below (**see I.5**).

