Recruitment and informed consent: We will obtain online informed consent prior to providing the self-administered online questionnaires and collection of any automated collection of process data. Online informed consents will be provided in two ways: (1) A recorded video of the informed consent text by a Peer will be displayed and (2) the same information will be provided in a easy to read text format.^{160,164} A link for emailing or direct messaging and contact information with the PI and Research Assistant's office phone numbers will be displayed for potential participants to ask any questions they may have. To indicate consent, an individual will then click a box attesting to their consent and then clicking a "submit" button. After consenting, participants will be taken directly to a baseline assessment survey and after completing the survey, participants will be asked to join the private social media E-PrEP (intervention) or BxNow (control condition) groups on one or more of three social media sites.

Protection against risk: Questions pertaining to substance abuse, sexual activity and identities requires special sensitivity to issues of confidentiality. Participant confidentiality will be carefully protected. We will institute the following processes to ensure confidentiality is maintained:

1. We will obtain a Certificate of Confidentiality to protect participants' potentially sensitive information.
2. **Publication/presentation of results:** We will not identify subjects by name, online screen-names or IDs.
3. **Managing the matter of anonymity and/or false information of research participant/study:** We will conduct Face-to-Face meetings with Peers and the supporting research team to discuss site activity, messaging, and member profiles and scan content for false information. To protect anonymity while retrieving viable information, research participants will be able to join SM sites using pseudonyms and will be asked to provide basic demographic information including age, email address and ethnicity over the

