		To assist prospective PrEP users with cost, commercial insurance and Medicaid in New York and other States cover PrEP and access is rapidly growing. Additionally, the manufacturer of emtricitibine-tenofovir (Truvada) has implemented a patient assistance program to help patients without coverage or who cannot afford PrEP; this program extends to ALL including immigrants or undocumented individuals.
Fairness	Control group participants may not be exposed to potentially beneficial information about HIV, and may not benefit from PrEP uptake.	At the beginning of the trial, the control group will be given basic information about the trial. At the end of the 12 week follow-up period (end of trial and follow-up), we will provide access to all educational intervention materials to control group participants and continue to be accessible to answer any questions, concerns, and provide access to Montefiore's linkage-to-care coordinator.
Confidentiality	There is little control over privacy in situations where evaluation data are collected online; Some social media sites have been involved in public scrutiny over confidentiality of its' site members.	
Participants will be asked to join a private group or feed on a social media platform. We do not invite participants to become a 'friend' or an associated with study staff (i.e. PI, RA, Consultants), thus we have no access to personal information on profiles, other than what is already publicly available online. We will also inform all participants after they join on how to monitor and change their privacy settings, further enhancing their control.
 
While Peers will be recruiting participants for this study (as they do now for many in-person studies), Peers will have no access to participants' survey data.
 
Participants will be able to post information to the private study groups/feeds as they see fit – sharing as much or as little as they prefer; study sites will be monitored multiple times each day and incorrect or inappropriate information removed.

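### Participants are asked to join groups named E-PrEP or BxNow before the only privacy-setting guidance described, so the sequence and the unequal names weaken the plan's own confidentiality safeguard

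*Combined protocol and SAP*

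**What the plan says.** **Order of steps.** Recruitment item 9 under Procedures for General Participants takes a person from online consent to the baseline survey. After that, "participants will be asked to join the private social media E-PrEP (intervention) or BxNow (control condition) groups", on at least one of three platforms. I.1.2 (Recruitment, item 9) and I.5 (Recruitment and informed consent) repeat this.

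**Names.** Under Setup of intervention sites, the team will "establish 'E-PrEP' and 'BxNow' (control) private virtual communities (e.g closed Facebook group, private Twitter feed, private Tumbler blog". No section gives the groups any other display name.

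**Privacy guidance.** The Confidentiality row of the I.8 table says: "We will also inform all participants after they join on how to monitor and change their privacy settings". No earlier guidance on participants' own settings is described.

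**Acknowledged risk.** I.4 names as its second primary risk a "breach of confidentiality leading to disclosure of an individual"'s "participation in a HIV prevention intervention". I.3 adds that being revealed as a participant could bring further stigma.

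**Safeguards.**
- The communities are closed or private (Setup of intervention sites).
- Activity is to stay private to study participants, and the study sites' privacy settings are reviewed at least every four weeks (Data Security; I.5 item 8).
- I.5 item 3 states that "research participants will be able to join SM sites using pseudonyms".
- Participants are not asked to befriend study staff (I.8).

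**Analysis.** The number of platforms each participant joins is recorded (Data Collection). The Analytic Plan uses the number of sites joined as a subgroup variable and possible covariate, and counts participation as a feasibility measure. It specifies no comparison of joining by arm and no handling of consented people who never join.

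**The concern.** The plan treats exposure as a participant in HIV prevention as a main harm. Yet participants take the step that creates membership before they receive the privacy help described, and in one arm that membership sits under a name containing PrEP. Guidance given afterwards cannot undo whatever was visible in between.

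There is also a statistical side. A participant's arm is fixed by the Peer's allocation, or by assignment to a Peer's group for those recruited through ads, so joining comes after assignment. If the E-PrEP name puts off some people who would have joined a neutrally named group, uptake of the allocated content differs by arm. The effect on the primary comparison then depends on whether non-joiners still answer the surveys and how they are analysed. The trial is meant to measure feasibility and supply an effect size for a later application (Power Analysis), so unreported differences in joining would carry into both.

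**Working it through.** **1. The passages side by side**
- Sequence: consent, T1, request to join, then privacy guidance.
- Labels: E-PrEP against BxNow, with no neutral display name mentioned.
- Visibility to outsiders: not stated. The groups are private, but no section says whether a group's name or member list can be seen from outside. I.2 accepts that process data, including screen names and connection to a Peer, are public or could be.
- Visibility to co-members: Peers recruit from their personal online networks (Recruitment, item 2), supplemented by Facebook ads, and I.2 counts mutual friends. A closed group does not hide a member from acquaintances inside it. This holds in both arms, but only one group name states PrEP.

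**2. The plan's sample size, to fix the numbers analysed**

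Inputs (Power Analysis): 20% versus 5%, two-sided 0.05, 80% power, up to 20% attrition, total 220.

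With p1 = 0.20, p2 = 0.05 and mean 0.125:

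n = [1.96·√(2·0.125·0.875) + 0.842·√(0.20·0.80 + 0.05·0.95)]² / 0.15² ≈ 75.1, or 76 per arm.

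Continuity correction: (n/4)·[1 + √(1 + 4/(n·0.15))]² ≈ 88 per arm, 176 in total. Then 176/0.80 = 220, an exact match. Without the correction the total is 152/0.80 = 190, which does not match. Participants are treated as independent, with no allowance for clustering by Peer. The same holds in steps 3 and 4.

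Analysed per arm after 20% attrition: 88 from 220, or 96 from the enrolment target of 240.

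**3. If non-joiners answer and stay in their arm: dilution**

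Assumptions: a share j of the E-PrEP arm joins, joiners respond at 20%, non-joiners respond at the control rate of 5%, and BxNow stays at 5%. The E-PrEP rate is then 0.05 + 0.15·j. Continuity-corrected power:

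| Joining, E-PrEP arm | E-PrEP rate | Power, 88 per arm | Power, 96 per arm |
|---|---|---|---|
| 100% | 20.0% | 80% | 84% |
| 90% | 18.5% | 73% | 77% |
| 80% | 17.0% | 64% | 68% |
| 70% | 15.5% | 54% | 58% |

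**4. If the extra non-joiners drop out of the data: inflation**

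Assumptions: no true effect, a common intention rate p, and an extra fraction d of the E-PrEP arm that does not join. All of these extra non-joiners are non-intenders and none answers T2. The observed E-PrEP rate is p/(1−d), so the false difference is p/(1−d) − p:

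| p | d = 5 points | d = 20 points |
|---|---|---|
| 5% | 0.05/0.95 − 0.05 = 0.3 points | 0.05/0.80 − 0.05 = 1.3 points |
| 10% | 0.5 points | 2.5 points |
| 20% | 1.1 points | 5.0 points |

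The planned effect is 15 points. The documents give no joining rates, so j and d are ranges chosen for illustration.

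**The case against.** Several stronger readings are tempting, and the documents do not support them.

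- **That joining is compulsory.** Participants are asked to join. It is fair to add only that no other way of receiving the content is described.
- **That joining reveals participation to outsiders.** This turns on platform settings the documents do not give. The safeguards are real and reduce the risk. Exposure to acquaintances in the same group is better supported, though those people are enrolled in the same study.
- **That the target population would avoid a PrEP-named group.** Background describes men "who are unlikely to present in-person to LGBT- or HIV-affiliated settings". That concerns attendance in person, and the plan offers social media as the remedy. It is not evidence about a private online group.
- **That PrEP is met only in the E-PrEP arm.** Both arms answer PrEP items at T1 (Table 2), before being asked to join, and BxNow carries basic PrEP information (Developing BxNow; I.6). Only a residual effect of the name itself is left.
- **That the result will be biased towards E-PrEP.** Surveys are held away from the social media sites (I.8, HIPAA row) and incentives follow survey completion (Compensation), so a non-joiner can still respond. Dilution is at least as plausible as inflation.

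It can also be said that naming is a matter of branding, that Peer input shapes format and delivery, and that the documents do not rule out neutral display names. That is fair. What stands is narrower: the stated order puts guidance after the exposure it is meant to limit, the stated names are unequal, visibility of membership is left open, and joining is not compared by arm.

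**Conclusion.** The point holds as an inexpensive improvement, chiefly on confidentiality grounds. The order of steps and the unequal names are in the text, and they work against a safeguard for a risk the plan itself ranks as primary. The existing protections lessen that risk without saying who can see a group's name or members.

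The statistical argument is secondary. Differential joining is an inference with no data behind it, and its direction is uncertain. At the plan's 5% rate, inflation is about 0.3 to 1.3 points for 5 to 20 points of extra non-joining, even if every extra non-joiner is a non-intender who does not respond. That is small beside 15 points; the 5.0-point figure needs a 20% rate with no effect, four times the planned control rate. Dilution could cost more: 80% power becomes 73% at 90% joining and 64% at 80%, with 88 per arm and non-joiners at 5%. A reader might infer that the plan will produce a spurious benefit; the documents do not support that.

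The consent form text was not examined. If it already gives privacy-setting guidance, the gap in timing is smaller than described here.

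**What to change.** 1. Show the privacy-setting instructions from the I.8 Confidentiality row on a screen after T1 and before the join link. State there who can see the group's name and its members.
2. In Setup of intervention sites, and wherever the join step is described (Recruitment item 9, I.1.2, I.5), give both arms' groups, feeds and blogs matched neutral display names with no PrEP or HIV term. Keep E-PrEP and BxNow as internal labels.
3. In the Analytic Plan, tabulate joining among T1 completers by arm, using the platform counts already collected.
4. State that consented participants who do not join stay in their assigned arm for analysis. This does not by itself resolve missing surveys among non-joiners, so report survey response by joining status and arm alongside it.

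The cost is one screen in the online flow, a renaming before launch, and a few sentences and a table in the analysis plan. No new data collection is needed. The downside is that the E-PrEP brand no longer appears on the group name.

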Intervention Procedures: After target enrollment (n=240) is reached, YMCSM Peers will begin the intervention by posting materials according to the timeline developed in the ongoing E-PrEP content project. We will hold weekly project meetings (on different days) with Peers assigned to both E-PrEP and BxNow to ensure appropriate implementation, and to discuss logistical, ethical, or other issues that arise. For participants in the BxNow control arm, Peers will post about general health topics unrelated to HIV or sexual health (e.g. fitness, nutrition, smoking). If a control participant posts a question about PrEP, Peers will refer the individual to the CDC PrEP information site or answer the question privately. Content for both arms will be posted over a 6 week period, and outcome data will be collected via online surveys at baseline, 6, and 12 weeks and after 36 weeks (Table 13). Participants will be given \$20, \$30, and \$40 and 20 online gift-cards or through a Clincard as incentives after completion of assessments at T1, T2, and T3, and T4 respectively.

Anticipated components of E-PrEP: Potential components are listed in Table 2. *However, the exact contents, formats, and mode and timing of delivery of E-PrEP will be informed by input from Peers.*¹²³ We have successfully used this approach in *theSEXword* pilot, with ongoing engagement by participants. We will develop all components for both E-PrEP and the control condition (BxNow), and will also create an intervention activity guide for all 6 weeks, but the exact timeline for intervention delivery will be determined based on findings from Aims 1 and 2. We will thus standardize E-PrEP in its mode of delivery, types of digital media and contents, message framing, and sequence of topics posted and discussed, but Peers will tailor the exact language of posts based on their communication style. Components will be interactive wherever possible; for example, to target a factor such as perceived low risk, participants might assess their risk in an interactive poll, see results in real-time, compare themselves to others, and be engaged by Peers in discussions about risk. To address barriers to access, we might develop a brief time-elapsd video showing where and how to register at a clinic to obtain PrEP. All materials, including assessments, will be smartphone friendly, as most participants use mobile devices.

Table 1. Intervention Timeline

Component	Week	-4	0	6	12	36+
Participant Recruitment						

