Compensation: Participants will be given \$20, \$30, and \$40 and \$20 as incentives after completion of assessments at baseline (T1), 6 weeks (T2), and 12 weeks(T3), and post 36 weeks (T4) (respectively). The participants will be given the choice to receive their incentives either via e-codes, Amazon online-gift cards, or by receiving a Clincard.

Data Collection:

We will collect three general types of data: 1) online processes (e.g. referral source, # of platforms joined by each participant); 2) measures of engagement with intervention components (e.g. # of views, time spent online); and 3) measures of outcome and independent variables, collected through online surveys at the ~~four~~three time points (see Table 2). To help assess both degree of exposure to intervention components and possible contamination between the two conditions, the surveys at 6 weeks (T2), ~~and~~ 12 weeks (T3) will display random samples of study and non-study graphics and posts and ask participants if they recall seeing them, with E-PrEP materials embedded in the choices.^{106,119,141}

Table 2. Data Collection					
Measures	Week	0	6	12	36+
PrEP intention, use, knowledge, attitudes		x	x	x	x
Perceived PrEP attributes		x	x	x	
HIV testing, risk behaviors		x	x	x	
Peer affinity and network data		x	x	x	

Table 2. Data Collection					
Measures	Week	0	6	12	36+
PrEP intention, use, knowledge, attitudes		x	x	x	x
Perceived PrEP attributes		x	x	x	
HIV testing, risk behaviors		x	x	x	
Peer affinity and network data		x	x	x	
Sociodemographic Factors		x			
Sexual Orientation		x			
Healthcare access		x	x	x	
Substance use		x	x	x	
Perceived risk, stigma		x	x	x	
Social media engagement		x	x		
Intervention exposure			x	x	

Data Security:

In order to securing information over the Internet and social media, and protecting participant data, an electronic, password protected and encrypted system will be developed to store analyses, and social media activity will remain private to study participants.¹⁶⁴ Research participants will be informed of how communications are recorded and stored during the online informed consent process. Due to the ever-changing and evolving nature of privacy issues on social media sites, we will review privacy settings for all social media study sites at least every four weeks and adjustments will be made to the study sites as necessary.

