1. <https://www.qualtrics.com/support/survey-platform/survey-module/survey-options/survey-protection/#PreventingRespondentsFromTakingYourSurveyMoreThanOnce>

Furthermore, we will download the raw data and store it in a password protected *and* encrypted file on the office computer of [name]. Only the PIs and research study staff will have access to the full data-set.

Analytic Plan: Our *primary outcome* will be *intention to use PrEP*,⁸³ which we consider a predictor of subsequent use,¹⁴² and will be measured using a Likert scale. We will use ‘intention’ as a proxy given the low likelihood of actual PrEP use.^{83,132,143} *Secondary outcomes* will be PrEP use, knowledge,¹⁴³ perceptions about PrEP¹³⁴ and HIV testing- and risk-behaviors.¹⁴⁴ *Covariates*^{80,81,143,145-148} will include access to medical care (including HIV/STI testing), sexual orientation, HIV and PrEP related stigma, substance use, sociodemographic factors,¹⁴⁴ social media engagement and network data,^{149,169} and perceived affinity to the referring Peer.¹⁵⁰ First, we will compare groups for equivalence at baseline, using chi-square or t-tests as appropriate. In addition, we will determine whether subgroups (e.g., grouped by number of social media sites joined, social media platform(s) used, peer referent, race/ethnicity, and sexual orientation) differ with respect to the primary and secondary outcomes. Relevant differences will be used as covariates in subsequent models. At each time point, we will examine change in our primary outcome variable (*intention to use PrEP*) by using a traditional two-sample test of proportions. To compare differences in outcomes between arms over time, we will use

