Potential Benefits to control condition participants: Participants in BxNow (attention matched control condition) will receive non-overlapping health information about general health topics including physical fitness and nutrition during the 6 week intervention period and linkage-to-care information for comprehensive primary care which would include access to providers who prescribe PrEP. Additionally, they will receive basic information about PrEP and links to further information and local resources at the start of the trial. At the end of the follow-up period (at 12 weeks), after completing the final survey, participants will be given access to all E-PrEP components, information about HIV/STI testing, risk reduction strategies, local resources for sexual health, and information about PrEP. We agree with our current YMCSM Peers and YMCSM community advisory board who advocated for this approach to address issues of *Fairness* and *Justice*, as HIV is a huge burden for this community.

In addition, at the end of the follow-up period (after 12 weeks), both intervention and control groups will be provided again with information about in-person services and we provide direct access to the Adolescent AIDS Program linkage-to-care coordinator and Montefiore Medical Center's primary care linkage-to-care coordinator.

I.7. Risk/benefit ratio. E-PrEP has the potential to increase reach of HIV prevention programs and services, and reduce HIV risk behaviors in YMCSM, but will require pilot testing and refinement. If effective, E-PrEP could be broadly implemented by health centers and community-based organizations, and reduce HIV transmission and promote healthy behaviors. Given the steps that we will take to minimize the chances of breach of confidentiality, participating in this study presents low risk and the risk/benefit ratio is favorable.

I.8 Ethical Principles considered for the online E-PrEP intervention (adapted from Bull et al. 2011)¹⁶⁴

Ethical principles and issues	Issues pertinent to the E-PrEP intervention	How E-PrEP will address the issue

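### Random recall items shown at both T2 and T3 leave control recall at T3 ambiguous as a contamination measure, and the unstated place of the recall block leaves the intention outcome open to cueing

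*Combined protocol and SAP*

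**What the plan says.** The Data Collection section states that the T2 and T3 surveys "will display random samples of study and non-study graphics and posts and ask participants if they recall seeing them", "with E-PrEP materials embedded in the choices". The aims are to gauge exposure to the intervention and "possible contamination between the two conditions". No arm is exempted. Table 2 lists intervention exposure at weeks 6 and 12, and PrEP intention, use, knowledge and attitudes at weeks 0, 6, 12 and 36+.

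On timing, Intervention Procedures says "Content for both arms will be posted over a 6 week period", so T2 falls at the end of posting and T3 six weeks later. The primary outcome is intention to use PrEP. The Analytic Plan examines it at each time point and in repeated-measures models. The Power Analysis is for the 6-week comparison; for 12 weeks it claims adequate power but gives no figure.

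On control content, section I.6 says BxNow participants "will receive non-overlapping health information about general health topics" during the intervention period. The section on developing BxNow describes general health content "but will also include basic information on PrEP as well as referral resources", and adds that "after trial end (12 weeks), BxNow participants will be exposed to all E-PrEP components".

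The documents do not say whether T3 items exclude those shown at T2, whether the recall question excludes the surveys as a source, where the recall block sits relative to the intention items, or how the recall answers will be analysed.

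**The concern.** A recall check for contamination works by showing control participants material they were not meant to see. The first showing, at T2, is clean: a yes answer can come only from real exposure or false memory. The second showing, at T3, is not, because the T2 survey has become another place where a control participant could have seen the item. That participant can answer truthfully and still be counted as contaminated through the network.

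The second issue is order within a survey. If E-PrEP graphics come before the intention items, they can prompt the answers at that wave. Both arms see them, but the material is new mainly to controls, so the likelier direction is a smaller difference between arms.

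Two readings are at stake. Contamination could look larger at 12 weeks than it was, and a weak result could then be put down to network overlap. At 6 weeks, the powered comparison could be affected by the instrument itself.

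**Working it through.** **1. Are control participants shown E-PrEP items at T2?** Yes. Detecting contamination between conditions requires it, and the text exempts no arm.

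**2. Which comparison does the plan power?** Inputs from the Power Analysis: 20% against 5%, two-sided 0.05, 80% power, up to 20% attrition, total 220.

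- Uncorrected: n = [1.960 × √(2 × 0.125 × 0.875) + 0.842 × √(0.20 × 0.80 + 0.05 × 0.95)]² / 0.15² = 75.1 per arm.
- Continuity-corrected: n′ = (n/4) × [1 + √(1 + 4/(n × 0.15))]² = 87.9, so 88 per arm and 176 completers.
- With attrition: 176 / 0.80 = 220, which matches the plan.

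This calculation is for T2. A display inside the T2 survey can reach it only if the recall block precedes the intention items.

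**3. How far can T3 recall be inflated?** The documents give no figures, so these are illustrations at item level. Let c be the true proportion of control participants exposed to an item outside the surveys, o the chance that a T3 item was also shown to that person at T2, and r the chance of recognising it six weeks later. Then

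apparent exposure at T3 = c + (1 − c) × o × r.

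With c = 5% (assumed):

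| Overlap o | r = 10% | r = 50% |
|---|---|---|
| 0 | 5.0% | 5.0% |
| 25% | 5 + 95 × 0.25 × 0.10 = 7.4% | 5 + 95 × 0.25 × 0.50 = 16.9% |
| 50% | 9.8% | 28.8% |
| 100% | 14.5% | 52.5% |

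The result turns on o. If 5 items were drawn afresh from a pool of 30 at each wave (assumed), the expected share of T3 items already shown at T2 would be 5/30 = 17%. If a single random sample were drawn and used at both waves, o would be 100%. If T3 items were drawn only from those not shown at T2, o would be 0. The plan's wording allows all three.

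**4. Can the foils separate the two sources?** Suppose foils repeat and are re-recognised at the same rates as E-PrEP items, and nobody meets them outside the surveys. Foil recall at T3 is then o × r, and

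E-PrEP recall − foil recall = c + (1 − c) × o × r − o × r = c × (1 − o × r).

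With c = 5%, o = 25% and r = 50%, this is 5% × 0.875 = 4.4%, close to the true 5%. The foils could therefore remove most of the ambiguity, but only under those conditions and only if the comparison is made. The plan specifies neither.

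**5. Is T2 recall affected?** No recall items are shown before T2, and posting has ended by then. T2 recall therefore covers the whole posting period and has no earlier survey display to confuse it.

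**The case against.** The case against is substantial. The samples are random, so T3 items may differ from T2 items, and with no overlap the T3 problem disappears. Non-study foils are in both surveys. T2 recall is clean. Section I.2 adds automated data on exposure to study materials, likes, shares and connection to a Peer, so contamination does not rest on T3 recall alone. Controls already receive basic PrEP information and answer PrEP questions at every survey, so a brief display may add little. The study's primary purpose is feasibility and an effect-size estimate.

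Most of this stands, and it limits the point. It does not remove it: random draws can repeat items unless repeats are prevented, and the foils help only if the analysis uses them.

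A reader might infer more than the documents support:

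- **That T3 recall is worthless.** This is not established. It depends on an overlap that is not stated, and foils and T2 recall remain available.
- **That a calculable amount of power is lost.** No document gives a size for cueing or a power figure at 12 weeks. Any figure would rest on an invented shift in control intention.
- **That the chance of at least one repeated item measures the harm.** It is not a false-recall rate, and it overstates the matter if every pool item is treated as E-PrEP when the samples mix study and non-study items.
- **That the survey contradicts section I.6.** The statement there about non-overlapping information describes BxNow content, not survey content, and the same paragraph says controls receive basic PrEP information.

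**Conclusion.** The point holds in a limited form. As written, a control participant's T3 recall of an E-PrEP item cannot be assigned to network contamination rather than to the T2 survey. The size is unknown: under the assumptions shown, inflation runs from nil with disjoint items to 2 to 12 percentage points at 25% overlap, and more if items are reused in full. T2 recall is not affected.

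The risk to the primary outcome is conditional. If the recall block precedes the intention items, it can cue intention at that wave, including the powered 6-week comparison. If it follows them, the 6-week comparison is untouched.

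A separate possibility, that the T2 display cues control intention at T3, cannot be excluded. It may be small, given the PrEP information controls already have. T4 is not a clean comparison in any case, because controls receive the E-PrEP components after week 12.

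This is a cheap improvement worth making before T2 is fielded. It does not invalidate the design.

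**What to change.** - Place the recall block after all PrEP outcome items in each survey, with no back-navigation.
- Draw each participant's T3 items from those not shown to that participant at T2.
- Word the question to ask about items seen outside the study surveys.
- State in the Analytic Plan that recall of E-PrEP items among controls will be compared with recall of foils, and that T2 recall is the main contamination measure, with T3 recall as supporting information.
- Record as a limitation of the 12-week comparison that controls were shown some E-PrEP items at T2. The steps above protect intention within each survey and T3 recall; they do not remove possible cueing of control intention between T2 and T3.

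The cost is survey programming and a few sentences in the plan, with no change in sample size. The downside is a smaller pool of items for T3.
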